3.3 Derivation of primary variable

The primary efficacy variable is the pre-bronchodilator (BD) forced expiratory volume in the first second (FEV₁) (L). Pre-BD FEV₁ (L) will be measured by in-clinic spirometry at visits SV1, SV2, SV4, SV6, SV7, SV8, SV9, SV10, SV11, SV12 and E/D. The primary efficacy endpoint is the change from baseline to Week 16 in pre-BD FEV₁ (L).

3.4 Derivation of secondary variables

3.4.1 Pharmacokinetics (PK)

Serum samples will be collected for measurement of serum concentrations of MEDI3506 at visits SV4, SV6, SV7, SV8, SV9, SV10, SV11, SV12 and E/D. Additional details are provided in Section 3.1.5.

3.4.2 Immunogenicity (serum)

Blood samples for determination of anti-drug antibodies (ADA) in serum will be assessed at visits SV4, SV6, SV7, SV8, SV9, SV10, SV12 and E/D.

3.4.2.1 ADA definitions

ADA detection at sample level:

- A sample is considered to be ADA positive if the titre is greater than or equal to the minimum required dilution (MRD) of the assay.
- A sample is considered to be ADA negative if the titre is <MRD of the assay.

ADA detection at participant level:

- A participant is considered ADA positive if at least one collected sample is tested positive at any time during the study, including baseline and/or post-baseline (see definition for ADA prevalence in Section 3.4.2.2).
- A participant is considered ADA negative if collected samples are tested negative at all timepoints, including baseline and post-baseline.

Subjects with a missing baseline ADA assessment should be assumed to be ADA negative as a conservative approach to ensure that all subjects are included in all analyses.

Treatment-related ADA development at participant level:

Treatment-emergent ADA positive (TE-ADA+) is defined as being either of treatment-induced ADA positive (ADA negative at baseline and at least one post-baseline ADA positive) and treatment-boosted ADA positive (ADA positive at baseline and baseline titre is boosted by greater than the variability of the assay (ie ≥ 4 -fold increase) at ≥ 1 post-baseline timepoint). Treatment-emergent ADA negative (TE-ADA-) is defined as ADA positive but not fulfilling the definition of TE-ADA positive.

The median of maximum titres is calculated based on the maximum titre for each ADA positive participant within each treatment group (including baseline and post-baseline measurements).

3.4.2.2 Categories of ADA responses

Baseline is defined as the last ADA assessment prior to the first dose of investigational product (IP).

Numbers and proportions of:

- Participants who are ADA positive at any time during the study, including baseline and/or post-baseline (also generally referred to as ADA positive). The proportion of ADA-positive participants in a population is known as ADA prevalence.
- Participants who are ADA negative at all assessments, including baseline and post-baseline (also generally referred to as ADA negative).
- Participants who are ADA positive at baseline only.
- Participants who are ADA positive at baseline and at least one post-baseline assessment.

- Participants who are treatment-emergent ADA positive (see definition in Section 3.4.2.1), reported overall and separately as treatment-induced and treatment-boosted subjects. The percentage of TE-ADA+ participants in a population is known as ADA incidence.
- Participants who are treatment-emergent ADA negative (see definition in Section 3.4.2.1).
- Participants who are persistently ADA positive, which is defined as ADA negative at baseline and having at least 2 post-baseline ADA positive measurements with ≥ 16 weeks between first and last positive, or an ADA positive result at the last available post baseline assessment.
- Participants who are transiently ADA positive, defined as ADA negative at baseline and at least one post-baseline ADA positive measurement and not fulfilling the conditions for persistently positive.
- Participants who are ADA positive with maximum titre $>$ median of maximum titres.

3.4.3 Asthma control questionnaire-6 (ACQ-6)

The questionnaire will be completed using the eDiary in accordance with the SoA of the CSP.

In the ACQ-6, participants are asked to recall how their asthma has been during the previous week by responding to one BD use question and 5 symptom questions. Questions are weighted equally and scored from 0 (totally controlled) to 6 (severely uncontrolled). The mean ACQ-6 score is the mean of the responses. If response to any of the questions is missing, the ACQ-6 score will be missing. Mean scores of ≤ 0.75 indicate well-controlled asthma, scores between >0.75 and <1.5 indicate partly controlled asthma, and scores ≥ 1.5 indicate not well-controlled asthma (Juniper et al 2006). Individual changes of at least 0.5 are considered clinically meaningful.

The key outcome variable for the ACQ-6 will be the change in mean score from baseline to Week 16. The change in mean score from baseline to each of the post-randomisation assessments will also be derived (see Section 3.1.3).

Other variables based on ACQ-6 to report include:

- Proportion of participants with a decrease in ACQ-6 score of ≥ 0.5 from baseline to Week 16 (Yes=1/No=0):
 - Yes: change from baseline ACQ-6 score to ACQ-6 score at Week 16: ≤ -0.5 .
 - No: change from baseline ACQ-6 score to ACQ-6 score at Week 16: > -0.5 .
- Proportion of participants achieving ACQ-6 well controlled status (Yes=1/No=0):
 - Yes: ACQ-6 score at Week 16 ≤ 0.75 .
 - No: ACQ-6 score at Week 16 > 0.75 .

Participants with missing or non-evaluable ACQ-6 score will be considered as not achieving ACQ-6 response.

3.4.4 St George's respiratory questionnaire (SGRQ)

The SGRQ is a 50-item PRO instrument developed to measure the health status of subjects with airway obstruction diseases (Jones et al 1991). The SGRQ yields a total score and three domain scores (symptoms, activity, and impacts). The total score indicates the impact of disease on overall health status. This total score is expressed as a percentage of overall impairment, in which 100 represents the worst possible health status and 0 indicates the best possible health status. Likewise, the domain scores range from 0 to 100, with higher scores indicative of greater impairment. Specific details on the scoring algorithms are provided by the developer in a user manual (Jones and Forde 2009). The principle of calculation of total score and domain scores in accordance with user manual are provided in [Appendix A](#).

The SGRQ will be completed using the eDiary in accordance with the SoA of the CSP, and a 4 week recall version will be used.

The key outcome variable for the SGRQ will be the change in mean total and domain scores from baseline to Week 16, but the change in mean total and domain scores from baseline to each of the post-randomisation assessments will also be derived (see Section 3.1.3).

Other variables based on SGRQ to report include:

- Proportion of participants with a decrease in SGRQ score of ≥ 4 points from baseline to Week 16 (Yes=1/No=0):
 - Yes: change from baseline SGRQ score to SGRQ score at Week 16: ≤ -4 .
 - No: change from baseline SGRQ score to SGRQ score at Week 16: > -4 .

Participants with missing or non-evaluable SGRQ score will be considered as not achieving SGRQ response.

3.4.5 Post-BD FEV₁

Secondary efficacy variable is the post-BD FEV₁ and will be measured by in-clinic spirometry at visits SV1, SV2, SV4, SV8 and SV10. The secondary endpoint is the absolute change from baseline to Weeks 8 and 16 in post-BD FEV₁ (L) (see Section 4.2.5).

3.4.6 Asthma CompEx

Asthma CompEx is a combination of exacerbations of asthma and diary events (ie, combination of eDiary variables). Asthma CompEx is a composite surrogate endpoint for exacerbations of asthma, recently developed by AstraZeneca (it is not yet a regulatory-approved clinical endpoint).

Diary events are defined by the threshold and slope criteria using the following morning/evening (AM/PM) diary variables:

- PEF (variable 1=V1= morning PEF; variable 2=V2= evening PEF).
- Symptom score (0 – 3) (variable 5=V5= morning symptom score; variable 6=V6= evening symptom score).
- Use of rescue medication (variable 3=V3= morning rescue medication usage; variable 4=V4= evening rescue medication usage).

A subject will be considered to have a CompEx event if the subject has one or both of the following:

- 1 An asthma exacerbation,
- 2 A diary event, which is defined as either the threshold criterion or the slope criterion (or both), as defined below, being met for ≥ 2 consecutive days.

For this purpose, “2 consecutive days” means strictly the same 2 consecutive days when assessing multiple requirements within those days. For the eDiary data (which is captured twice during the day), one day will be defined by the morning/evening pairing for consistency with published precedent for the CompEx endpoint. (Note: other eDiary endpoints in this trial will use an evening/morning pairing to define one day.) The morning eDiary recordings captured on the first day of treatment will not be included in the calculation of the CompEx endpoint.

Threshold criterion:

- (a) $\geq 15\%$ decrease from baseline in either morning (V1) or evening home-based PEF (V2),
and at least one of the following:
- (b) ≥ 1.5 doses increase from baseline in rescue medication in either the morning (for preceding night, V3) or evening (for preceding day, V4),
- (c) ≥ 1 score increase from baseline, or the absolute maximal symptom score, in either the morning (V5) or evening (V6).

For (b), the number of doses of rescue medication is defined as the number of puffs of inhaler recorded in the morning and evening, respectively.

For (c), the asthma symptom score (scored 0-3) as described in Section 3.6.2.1 (V1-V6), provided those non-missing values meet the criterion.

Slope criterion:

One of (a), (b) or (c) above is met for ≥ 2 consecutive days *and* the regression slope requirement over the preceding 5 days is also met.

The regression slope requirement in the preceding 5 days is that all of the following are met:

- Morning PEF slope $\leq -3\%/day$;
- Evening PEF slope $\leq -3\%/day$;
- Morning (preceding night) rescue medication slope ≥ 0.3 doses/day;
- Evening (preceding day) rescue medication slope ≥ 0.3 doses/day;
- Morning asthma symptom score slope ≥ 0.2 score/day;
- Evening asthma symptom score slope ≥ 0.2 score/day.

In all of the above cases, the regression slope is the point estimate of the slope obtained from a linear regression of the absolute values of each of the six variables (V1-V6) separately against day number, with no other variables included in the regression model.

For morning and evening PEF, the regression slope thus obtained will first also be divided by the baseline PEF value before applying the above criterion. The following table shows how the timing for the 5-day requirement for the regression slopes fits with the 2-consecutive day requirement, where “Day 0” here refers to the first of the 2 consecutive days (shaded) to be used each time the rolling 2 consecutive day assessment is made:

Table 3 Timing for assessment of CompEx slope criterion

	Day -4	Day -3	Day -2	Day -1	Day 0	Day 1
Threshold (a), (b), (c)					x	x
Slope	x	x	x	x	x	x

A regression slope will be calculated provided there are at least two non-missing values in the required 5 days. If one or more of the six variables above (V1-V6) does not have at least two non-missing values in the required 5 days, then the slope requirement therefore cannot be met.

The start date of a CompEx event is defined as the earliest of the exacerbation or objective deterioration start dates which meets the definition. Diary event start date is defined as the earliest Day 0 (in notation from Table 15) from any series of rolling 2 consecutive days which first qualifies using either the threshold or slope criterion.

The end date of a CompEx event is defined as the latest of the exacerbation or objective deterioration end dates which meets the definition. Diary event end date is defined as the latest Day 1 (in notation from Table 3 – Timing for assessment of CompEx slope criterion) from any series of rolling 2 consecutive days which last qualifies using either the threshold or slope criterion.

The event duration is defined as the end date minus the start date plus 1.

If the end date of the first CompEx event and the start date of the second CompEx event are less than 7 days apart for any subject, then these will be counted as one CompEx event.

For CompEx analyses, only on-treatment events (based on the period from baseline to last dose date +28 days) will be considered. A supplementary analysis including events in the period from baseline to end of follow-up (Week 24) will also be conducted.

Time-to-first event will be defined as: [Start date of first event or censoring – date of 1st dose] + 1.

Date of first event will be the first start date of a CompEx event as defined above. For participants who do not experience an on-treatment CompEx event, date of censoring will be the minimum between the date of last dose plus 28 days, and the last day of eDiary recording during the on-treatment period. For the analysis of CompEx during combined treatment and follow-up period, date of censoring will be the minimum between the date of end of study visit, and the last day of eDiary recording during combined treatment and follow-up period .

For recurrent events, there must be a gap of 7 days between events ie, at least 7 days between end date of first CompEx event and start date of second CompEx event. Events that occur closer in time will be collapsed into one event.

The time during the event and the 7 days after each event will not be considered when defining time at risk for the CompEx event rate. Time at risk will be defined as [Date of last treatment plus 28 days– date of 1st dose] + 1 – recovery time. For the analysis of CompEx during combined treatment and follow-up period, the time at risk will be defined as [date of end of study visit – date of 1st dose] + 1 – recovery time.

The annualised rate of asthma CompEx events, during intervention period (Baseline to last dose date +28 days) per participant will be calculated as:

Annualised rate of asthma CompEx events during intervention period =

Total number of asthma CompEx events

$$\frac{\text{Total number of asthma CompEx events}}{(\text{Date of last dose of IP} + 28 - \text{Date of the first dose of IP} - \text{recovery time} + 1)/365.25}$$

where the recovery time is defined as:

$$\sum_{i=1}^k [\min(i^{\text{th}} \text{ event end date} + 7, \text{date of last dose} + 28) - i^{\text{th}} \text{ event start date} + 1]$$

The annualised rate of asthma CompEx events, during intervention and follow-up periods (Baseline to Week 24) per participant will be calculated as:

$$\text{Annualised rate of asthma CompEx events during intervention and follow-up periods} = \frac{\text{Total number of asthma CompEx events}}{(\text{Date of last follow up} - \text{Date of the first dose of IP} - \text{recovery time} + 1)/365.25}$$

Where the recovery time is defined as:

$$\sum_{i=1}^k [\min(i^{\text{th}} \text{ event end date} + 7, \text{date of last follow up}) - i^{\text{th}} \text{ event start date} + 1]$$

Rolling windows of time:

The deterioration criteria for the individual diary variables are defined as a combination of threshold criteria and regression slope criteria during each rolling window. Each rolling window contains 6 consecutive days, including 2 consecutive days for threshold assessment (Window Day 0 and 1), and 5 preceding consecutive days for regression slope assessment (Window Day -4 to 0). For this purpose, “2 consecutive days” means the same 2 consecutive days when assessing multiple threshold requirements. Similarly, ‘5 preceding consecutive days’ means the same 5 preceding consecutive days when assessing multiple slope requirements.

Rolling Window	Study Day	1	2	3	4	5	6	7	8	n	n+1	n+2	n+3	n+4	n+5
1	Window Day	-4	-3	-2	-1	0	1									
	Threshold Assessment					x	x									
	Slope Assessment	x	x	x	x	x										
2	Window Day		-4	-3	-2	-1	0	1								

Rolling Window	Study Day	1	2	3	4	5	6	7	8	n	n+1	n+2	n+3	n+4	n+5
	Threshold Assessment						x	x								
	Slope Assessment		x	x	x	x	x									
3	Window Day			-	-	-	-	0	1							
	Threshold Assessment			4	3	2	1			x	x					
	Slope Assessment		x	x	x	x	x									
.....																
n	Window Day									-	-3	-2	-1	0	1	
	Threshold Assessment													x	x	
	Slope Assessment									x	x	x	x	x		

The deterioration criteria are assessed for a series of rolling windows over the entire study duration. For example, Window 1 includes ‘Study Day 1’ through ‘Study Day 6’, Window 2 rolls one day forward that includes ‘Study Day 2’ through ‘Study Day 7’, Window 3 rolls one day forward that includes ‘Study Day 3’ through ‘Study Day 8’, and so on so forth, as illustrated in the table below:

Table 46 Rolling windows of time

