3 OBJECTIVES AND ENDPOINTS

Table 4 Objectives and Endpoints

Objective	Endpoint
Primary	
To assess the effect of MEDI3506 compared with placebo on lung function, in adult participants with uncontrolled moderate-to-severe asthma.	As measured in clinic, change from baseline to Week 16 in pre-BD FEV ₁ (L).
Secondary	
To further assess the effect of MEDI3506 compared with placebo on lung function, in adult participants with uncontrolled moderate-to-severe asthma.	As measured in clinic, change from baseline to Weeks 8 and 16 in post-BD FEV ₁ (L).
To assess the PK of MEDI3506 in adult participants with uncontrolled moderate-to-severe asthma.	Serum MEDI3506 concentration-time profiles during the intervention and follow-up periods.
To assess the immunogenicity of MEDI3506 in adult participants with uncontrolled moderate-to-severe asthma.	ADA during the intervention and follow-up periods.
To assess the effect of MEDI3506 compared with placebo on asthma control in adult participants with uncontrolled moderate-to-severe asthma.	Change from baseline to Week 16 in ACQ-6 score. Proportion of participants with a decrease in ACQ-6 score of ≥ 0.5 from baseline to Week 16. Proportion of participants achieving ACQ-6 well controlled status (defined as ACQ-6 score ≤ 0.75 at Week 16).
To assess the effect of MEDI3506 compared with placebo on health status in adult participants with uncontrolled moderate-to-severe asthma.	Change from baseline to Week 16 in SGRQ score. Proportion of participants with a decrease in SGRQ total score of ≥ 4 points from baseline to Week 16.
To assess the effect of MEDI3506 compared with placebo on CompEx in adult participants with uncontrolled moderate-to-severe asthma.	Time to first CompEx event based on the period from baseline to Week 16. CompEx annualised event rate.
To assess the effect of MEDI3506 compared with placebo on concentration of FeNO in adult participants with uncontrolled moderate-to-severe asthma.	Percent change from baseline to Week 16 in concentration of FeNO in exhaled breath.

Table 4 Objectives and Endpoints

Objective	Endpoint
Safety	

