Period 4: Evening of Day 43 – Morning of Day 57	Week 8	57
Period 5: Evening of Day 57 – Morning of Day 71	Week 10	71
Period 6: Evening of Day 71 – Morning of Day 85	Week 12	85
Period 7: Evening of Day 85 – Morning of Day 99	Week 14	99
Period 8: Evening of Day 99 – Morning of Day 113	Week 16	113
Period 9: Evening of Day 113 – Morning of Day 127	Week 18	127
Period 10: Evening of Day 127 – Morning of Day 141	Week 20	141
Period 11: Evening of Day 141 – Morning of Day 155	Week 22	155
Period 12: Evening of Day 155 – Morning of Day 169	Week 24	169

The Early Discontinuation and unscheduled visits will be included when applying the visit windows to ensure that all available data are used in the analysis.

For bi-weekly summaries, the mean of all non-missing observations within an assigned window is calculated. If there are fewer than 10 completed days in the 14 day period (where a

complete day = entry from the evening AND the following morning) then the analysis value will be set to missing.

Finally, for the purpose of the statistical analysis, the assessments will be allocated to the study phase in which they are collected as reported below.

Table 2 Study phase windows

Study phase	Phase Window for Analysis (Days)
Pre-treatment	Prior to the first administration of investigational product (day <1 ^a)
On-treatment	≥ day 1 ^b to last dose date plus 28 days (included)
Follow-up	> last dose date plus 28 days

^a Includes all measurements collected before first dose of IP. If the measurement is collected on day 1 it cannot be determined if it was done before or after the first dose of IP (due to missing time and/or planned time point), then it will be considered as collected after first dose of IP.

^b Includes all measurements collected on the day of first dose of IP, at the time of IP intake and after.

Unless otherwise specified, the study phase will be mainly used for safety analysis (e.g., laboratories, adverse events) and for CompEx analysis.

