4.2.5.4 Analysis of Asthma CompEx

Time to first asthma CompEx event will be analysed using a Cox proportional hazard model, with group, background medication, geographic region and baseline ICS total daily dose as covariates (see Section 4.1.6). All available data from participants through Week 16 will be included. Additionally, the analysis of time to first asthma CompEx event will be repeated using all available data from participants through Week 24 (end of follow-up).

Time to first asthma CompEx will also be displayed in a Kaplan-Meier plot, including all data through to Week 24 (end of follow-up).

The asthma CompEx event rate will be analysed using negative binomial regression, with the log(follow-up time) included as an offset term and treatment group, geographic region, baseline ICS total daily dose as covariates (see Section 4.1.5). The dependent variable will be the number of asthma CompEx events through Week 16. All available data from participants through to Week 16 will be included, irrespective of whether they discontinued study intervention.

Additionally, the analyses of the asthma CompEx event rate will be repeated using all available data from participants through Week 24 (end of follow-up).

Asthma CompEx events will be also reported in listing for the ITT population.

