6 CHANGES OF ANALYSIS FROM PROTOCOL

This SAP is based on study protocol D9181C00001 Amendment V4.0 dated 08 March 2022. Any further amendment of the study protocol which can have an impact on the SAP will lead to an amendment of this document. Changes of analysis from D9181C00001 Amendment V4.0 dated 08 March 2022 are listed here below:

Section 3 Objectives and endpoints

- Time to first CompEx event based on the period from baseline to Week 16 is a secondary endpoint for this study. However, in this SAP, a supplementary analysis including events on the period from baseline to end of follow-up (Week 24) has been added.
- An additional spirometry parameter not part of the main study endpoints (FEF25-75%) will be explored.

Section 8.1.8.3 Asthma Control Questionnaire-6

In this section it is stated that “Mean scores of ≤ 0.75 indicate well-controlled asthma, scores between 0.75 and ≤ 1.5 indicate partly controlled asthma, and scores > 1.5 indicate not well-controlled asthma”. In this SAP it is specified that “Mean scores of ≤ 0.75 indicate well-controlled asthma, scores between >0.75 and <1.5 indicate partly controlled asthma, and scores ≥ 1.5 indicate not well-controlled asthma”.

Section 9.4.2.1 Primary Endpoint

In this section it is stated that the MMRM will include “fixed effects for baseline, visit, treatment and the baseline by visit and treatment by visit interactions”. In this SAP it is mentioned that the MMRM will additionally include background medication, geographic region and baseline ICS total daily dose as fixed effects. The same variables will be added as covariates to ANCOVA, logistic regression, Cox proportional hazards and negative binomial models.

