14.2 CompEx		
Table 14.2.5.1	Time to first Asthma CompEx event (days) based on the period from baseline to Week 16 - Cox-regression analysis	ITT population
Table 14.2.5.2	Time to first Asthma CompEx event (days) based on the period from baseline to Week 24 - Cox-regression analysis	ITT population
Figure 14.2.5	Time to first Asthma CompEx event (days), Kaplan-Meier plot	ITT population
Table 14.2.5.3	Asthma CompEx event rate through Week 16, summary statistics	ITT population
Table 14.2.5.4	Asthma CompEx event rate through Week 24, summary statistics	ITT population
Table 14.2.5.5	Asthma CompEx event through Week 16, negative binomial model	ITT population
Table 14.2.5.6	Asthma CompEx event through Week 24, negative binomial model	ITT population
14.2 AO		
Table 14.2.6.1	Airwave oscillometry parameters by visit, summary statistics	ITT population
Table 14.2.6.2	Change from baseline through Week 16 in airwave oscillometry parameters treatment comparisons, MMRM	ITT population
Figure 14.2.6	Change from baseline through Week 16 in airwave oscillometry parameters, LSM means (80% CI)	ITT population

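### SAP Section 3.4.6 limits the main CompEx analyses to last dose + 28 days, while the protocol and SAP Section 4.2.5.4 promise Week 16 data regardless of stopping (for the event rate), and Section 6 does not declare the change

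*SAP*

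**What the plan says.** **The restriction.** SAP Section 3.4.6 says: "For CompEx analyses, only on-treatment events (based on the period from baseline to last dose date +28 days) will be considered". The same section censors event-free participants no later than last dose + 28 days, ends the time at risk for the rate there, and caps recovery time there. SAP Section 3.1.4 defines the on-treatment phase with the same end point and adds: "Unless otherwise specified, the study phase will be mainly used for safety analysis (e.g., laboratories, adverse events) and for CompEx analysis".

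**The rule in the analysis sections.** For the event rate, SAP Section 4.2.5.4 says: "All available data from participants through to Week 16 will be included, irrespective of whether they discontinued study intervention". Protocol Section 9.4.2.2 contains the same sentence. For the other CompEx endpoint, Protocol Section 3 gives "Time to first CompEx event based on the period from baseline to Week 16", and SAP Section 4.2.5.4 says "All available data from participants through Week 16 will be included". No clause about discontinuation is attached to that second statement.

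**What is declared.** SAP Section 6 restates the protocol period ("Time to first CompEx event based on the period from baseline to Week 16 is a secondary endpoint for this study") and then announces only a supplementary analysis to Week 24. It separately declares extra covariates: "The same variables will be added as covariates to ANCOVA, logistic regression, Cox proportional hazards and negative binomial models". It says nothing about an on-treatment window. Appendix C still titles the rate output "Asthma CompEx event through Week 16, negative binomial model".

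**The concern.** The two data rules cannot both be followed for a participant who stops early or misses the last dose. One follows everyone to Week 16 whatever happens to treatment (a treatment-policy approach). The other stops counting 28 days after the last injection (a while-on-treatment approach). These answer different questions about a secondary endpoint.

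The excluded time comes only from participants who stopped or missed doses. Protocol Section 7.1 lists adverse events among the reasons for stopping, so that time may not be a random sample of follow-up. If the formulas in Section 3.4.6 are programmed, an on-treatment estimate will appear under a title that says Week 16, and the section meant to list departures from the protocol will not mention it.

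**Working it through.** The documents give no event rate, power or discontinuation rate for CompEx, so there is no planned figure to reproduce. The check compares the texts and then works out the days.

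**1. The rules side by side**

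| Item | SAP 3.4.6 | SAP 4.2.5.4 and the protocol |
|---|---|---|
| Events counted, rate | To last dose + 28 days | To Week 16, whether or not treatment stopped |
| Events counted, time to first event | To last dose + 28 days | To Week 16 |
| Censoring, time at risk, recovery time | Bounded by last dose + 28 days | No competing formula given |
| Listed in SAP Section 6 | No | Not applicable |

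**2. Day arithmetic**

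Inputs:
- Week 16 is Day 113 (Protocol Section 1.3, Table 2).
- Dose timing is redacted. SAP Section 3.5.2 schedules post-dose vital signs at SV4, SV7, SV8 and SV9, so dosing on Days 1, 29, 57 and 85 is inferred.

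Window end = last dose day + 28. Shortfall = 113 − window end.

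| Last dose (day) | Window ends (day) | Shortfall (days) | Share of 113 days |
|---|---|---|---|
| 1 | 29 | 84 | 74% |
| 29 | 57 | 56 | 50% |
| 57 | 85 | 28 | 25% |
| 85 | 113 | 0 | 0% |

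The Day 57 row needs no discontinuation: missing only the SV9 dose is enough. Protocol Sections 7.1.1 and 2.3.1.2 foresee missed and skipped visits.

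The window can also run long. Section 2.3.1.2 allows a visit to be moved by up to 14 days for pandemic reasons. An SV9 dose that late gives 85 + 14 + 28 = Day 127, which is 14 days past planned Week 16.

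**3. Person-time dropped**

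Assumptions: a share *p* of participants stop, equally often after dose 1, 2 or 3; all others are dosed on schedule; everyone could be observed to Day 113.

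Mean shortfall = (84 + 56 + 28)/3 = 56 days. Fraction dropped = *p* × 56/113 = 0.4956*p*.

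| *p* | Even spread | All stop after dose 3 (*p* × 28/113) | All stop after dose 1 (*p* × 84/113) |
|---|---|---|---|
| 5% | 2.5% | 1.2% | 3.7% |
| 10% | 5.0% | 2.5% | 7.4% |
| 20% | 9.9% | 5.0% | 14.9% |

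**4. Does another planned output supply the Week 16 result?**

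The supplementary Cox and negative binomial models run to Week 24 (Day 169), so they add up to 169 − 113 = 56 days after Week 16. The Kaplan-Meier plot to Week 24 shows first events before Week 16 but gives no hazard ratio or rate ratio. No output derived under Section 3.4.6 gives a Week 16 estimate regardless of discontinuation.

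**5. What data exist after stopping?**

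Protocol Section 7.1 keeps participants in the study. Section 8.1.5 requires exacerbations during treatment and follow-up to be entered in the eCRF, and under SAP Section 3.4.6 an exacerbation is a CompEx event by itself.

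Diary continuation is less clear. Protocol Section 8.1.8.1 asks for it generally, and SAP Section 3.6.2 uses diary data to Week 24. Protocol Table 2 refers to the intervention period, and Section 7.1 names only end-of-treatment and follow-up assessments.

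**The case against.** The best defence is that only Section 3.4.6 contains working formulas, so a programmer has one derivation to follow. The same end point is used for exacerbations in SAP Sections 3.6.4 and 4.2.6.3. It therefore looks like a deliberate stand-in for the 16-week intervention period, exact when dosing is on schedule. Off-treatment events still enter the Week 24 models and the event listing, which would expose a material effect. CompEx is secondary, in a proof-of-concept trial.

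Much of this stands, and it limits how serious the point is. It does not remove the contradiction. Section 4.2.5.4 states the opposite data rule for the rate in explicit words, and no precedence between the sections is given. If Section 3.4.6 prevails in practice, the analysis promised in the protocol is not produced and the departure is undeclared. The qualifier at the start of the Section 3.1.4 sentence does not help either, because Section 3.4.6 repeats the restriction in its own right.

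A reader might infer that events after stopping disappear from the report. They do not, for the reason just given. A reader might also infer that the explicit promise about discontinuation covers both CompEx endpoints. It is attached only to the event rate; for time to first event the conflict is with the Week 16 period and the general statement about available data.

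**Conclusion.** The point holds as an inconsistency within the SAP and an undeclared departure from the protocol, and it should be fixed. The textual finding is firm. The day counts rest on the inferred dosing days. The 2.5%, 5.0% and 9.9% of person-time rest on assumed stopping rates and an even spread over doses 1 to 3.

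The likely effect on the CompEx estimates is modest. A reader might go further and conclude that the results would be materially biased. The documents do not support that: they give no stopping rate, no CompEx event rate and nothing on how the effect changes after the last dose. Nor is there any bearing on the primary endpoint or on the two-step dose hierarchy in SAP Section 4.1.1, which concerns pre-bronchodilator FEV₁ only.

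**What to change.** **Preferred.** In SAP Section 3.4.6, define the main CompEx window as first dose to the earlier of Week 16 (the visit, or Day 113 if there is none) and study exit or death, regardless of discontinuation or missed doses. Use that one end date for event counting, Cox censoring, the negative binomial time at risk and the recovery-time cap. Count eCRF exacerbations through Week 16 in the main analysis even if the diary has stopped. Align Section 3.1.4. Keep last dose + 28 days as a labelled supplementary on-treatment analysis, and keep the Week 24 analysis. State whether diary entry continues after treatment stops.

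**Alternative.** If the on-treatment window is intended as the main analysis, declare it in Section 6, correct Section 4.2.5.4 and the Appendix C titles, and report the Week 16 analysis regardless of discontinuation beside it.

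**Cost.** SAP wording, a small amount of reprogramming around one end date, and one extra set of outputs. No new assessments are needed. If the diary is not kept after stopping, the gain is limited to eCRF exacerbations.
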